9. DATA HANDLING CONVENTIONS

9.1 REPEATED OR UNSCHEDULED ASSESSMENTS OF SAFETY PARAMETERS

If a patient has repeated safety assessments (e.g., for a lab parameter) prior to dosing of study drug, then the results from the final non-missing assessment made prior to the start of study drug will be used as baseline. If there is more than one safety measurement (e.g., for a lab parameter) at a postbaseline timepoint, only the last measurement will be used. All postbaseline assessments including unscheduled assessments, if any, will be used for notable value determination, and all assessments will be presented in data listings.

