BP = blood pressure; ECG = electrocardiogram; EDTA = ethylenediaminetetraacetic acid; h = hour; H = height; HBsAg = hepatitis B surface antigen; HCV = hepatitis C virus; HIV = human immunodeficiency virus; ICF = informed consent form; m = minute; NG = nitroglycerin; pd = postdose; PD = pharmacodynamic; pre = predose; W = weight

- Urine drug screen for selected drugs of abuse and alcohol breathalyzer screen
- For female patients, a negative serum pregnancy test must be documented at the Screening Visit, at Check-in with results available before dosing, and at the End of Trial Visit; a negative urine pregnancy test must be documented at the Follow-up Visit before nitroglycerin dosing.
- On in-clinic days, in the morning after voiding, before any water or food intake
- Patients must be supine for ≥ 5 m before the ECG recording (Note: if on initial ECG, QTcF is ≥ 450 msec for men or is ≥ 470 msec for women, the ECG will be repeated 2 more times, and the average of the 3 QTcF values will be used to determine the patient's eligibility); before blood draws where applicable
- Respiratory rate after the patient has been seated for ≥ 5 m
- After ≥ 8-h fast, after EndoPAT and BP/pulse measurements and before dosing, except at Follow-up Visit; left arm preferred. Urinalysis may be performed prior to EndoPAT and blood pressure assessments.
- Must fast ≥ 8 hours; left arm preferred

- h. Always precedes PD BP/pulse measurements and blood collections, except at Follow-up Visit;  $\geq 3$  h after any caffeine-containing foods/beverages,  $\geq 1$  h after allowed concomitant medications, after opportunity to void and then sitting quietly in a temperature-controlled room for  $\geq 15$  m; occlusion/finger measurement right arm/hand
- i. At Screening Visit & Check-in, supine BP is average of 3 measurements obtained at 2-m intervals after the patient has been lying quietly for  $\geq 5$  m; thereafter, 1 measurement after the patient has been lying quietly for  $\geq 5$  m.  
For supine to standing: patient must lie quietly for  $\geq 5$  m before supine measurements are taken, then assume sitting position for 1 m, and finally assume standing position for 2 m before standing measurements are taken.  
All measurements before blood draws where applicable; always left arm  
[REDACTED]
- k.  $\approx 2.7$ -mL blood sample in citrate tube at each timepoint; left arm preferred

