7.9.2 Clinical Laboratory Parameters

For each quantitative clinical laboratory parameter (including Hemoglobin A1c, fasting blood glucose, and serum insulin) descriptive statistics of the observed values as well as change from study baseline will be presented overall for each assessment timepoint. Change from time-matched baseline will also be presented for fasting blood glucose, and serum insulin by cycle group.

Parameter values will also be categorized as low, normal, or high based on reference ranges provided by the lab, and shifts from baseline to each later timepoint will be tabulated. If there is more than one measurement for a lab parameter at a postbaseline timepoint, only the last measurement will be used.

Individual patient plots of fasting blood glucose and serum insulin values will be plotted over time as patients escalate from placebo through the IW-1973 doses.

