7.9.3 Vital Signs Parameters

Vital signs evaluations at each assessment timepoint not included in the PD analyses and the corresponding change from study baseline will be summarized for each cycle group.

The number and percentage of patients who had a notable change from baseline in BP and pulse (based on the criteria in Table 3), will be presented by cycle group.

Table 3. Criteria for Notable Changes in Post-Baseline Vital Signs

| Vital Sign Parameter | Flag | Criteria* | |
|---|-------------|-----------------------|-----------------------------------|
| | | Observed Value | Change from Study Baseline |
| Supine/Standing Systolic Blood Pressure (mmHg) | High | ≥ 180 | Increase of ≥ 30 |
| | Low | ≤ 90 | Decrease of ≥ 30 |
| Supine/Standing Diastolic Blood Pressure (mmHg) | High | ≥ 105 | Increase of ≥ 20 |
| | Low | ≤ 50 | Decrease of ≥ 20 |
| Supine Pulse Rate (bpm) | High | ≥ 110 | Increase of ≥ 20 |
| | Low | ≤ 50 | Decrease of ≥ 20 |
| Standing Pulse Rate (bpm) | High | ≥ 120 | Increase of ≥ 30 |
| | Low | ≤ 50 | Decrease of ≥ 20 |

*A postbaseline value is considered as a notable value if it meets both criteria for observed value and change from baseline.

The number and percentage of patients who meet the following criteria at any postdose timepoint will also be summarized by cycle group:

- Orthostatic decrease in systolic BP of > 20 mmHg from supine to standing
- Orthostatic decrease in diastolic BP of > 10 mmHg from supine to standing
- Orthostatic increase in pulse of > 20 beats per minute from supine to standing

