7.9.4 ECG Parameters

For each ECG parameter, descriptive statistics will be presented by cycle group for each assessment timepoint. Change from study baseline (Day -1) statistics will also be presented for the predose assessment of each cycle. Shift tables from study baseline (Day -1) to the discharge visit (Day 19) for the overall ECG interpretation (normal, abnormal not clinically significant, or abnormal clinically significant) will be summarized for all subjects in the safety population. Change from time-matched baseline (placebo cycle) will be presented for QTc-F for each scheduled postdose assessment.

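### Under the last-value rule for repeated safety tests, a lab or QTcF abnormality that normalises on a same-timepoint retest, and is not reported as an AE, appears only in listings

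*SAP*

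**What the plan says.** For repeated safety assessments after baseline, SAP 9.1 states: "If there is more than one safety measurement (e.g., for a lab parameter) at a postbaseline timepoint, only the last measurement will be used". SAP 7.9.2 says the same for laboratory tests: "If there is more than one measurement for a lab parameter at a postbaseline timepoint, only the last measurement will be used". That sentence comes directly after the plan to classify each lab value as low, normal or high, under which "shifts from baseline to each later timepoint will be tabulated".

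SAP 9.1 then adds a safeguard: "All postbaseline assessments including unscheduled assessments, if any, will be used for notable value determination, and all assessments will be presented in data listings". The only notable criteria in the SAP are in Table 3 (SAP 7.9.3), for supine and standing blood pressure and pulse. The abbreviation list contains PCS (potentially clinically significant), but no such criteria are given for labs or ECG.

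Under SAP 7.9.4, ECG parameters get descriptive statistics by cycle, change from Day -1 at the predose assessments, and change from time-matched baseline for QTcF. The one ECG shift table covers the overall interpretation from Day -1 to Day 19.

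For baseline, SAP 9.1 takes the final non-missing predose result.

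**The concern.** Tests are often repeated because the first result looked wrong. If so, keeping only the last result is not neutral: it exchanges selected abnormal readings for retests that tend to lie nearer normal. The tables then lean towards showing no effect.

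The SAP appears to guard against this by using all assessments for notable values. That works for blood pressure and pulse. It does nothing for labs and QTcF, because there is no criterion for it to act on.

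Safety and tolerability is the first listed objective. The full lab panel is drawn on only two scheduled occasions after dosing starts, Day 19 and Day 32 (Protocol, Schedule of Events), so another scheduled draw offers little chance of showing the same abnormality.

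**Working it through.** The plan gives no figure to reproduce. The sample size was set without statistical calculation (SAP 4), and neither document states an abnormality rate or a retest rate. The check is a trace through the tables, followed by simple arithmetic.

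**Step 1. Where a repeated value ends up** (SAP 7.9.1 to 7.9.4 and 9.1; Protocol 3.7.3.7).

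| Measurement | Tables using the last value | All-values table | Other routes |
|---|---|---|---|
| Blood pressure, pulse | By-timepoint summaries | Yes, Table 3 | AE if clinically significant or needing intervention; listings |
| Laboratory tests | Descriptive, change, shift | None | Same |
| QTcF | Descriptive, change | None | Same |

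For labs and QTcF the only tabulated route that survives a normal retest is the AE route, which depends on the investigator's judgement. If the abnormality is not reported as an AE, only listings remain.

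**Step 2. Effect of one lab value.** Assume all 12 patients have a result at the timepoint. One abnormal first value kept gives 1/12 = 8.3% (exact 95% CI 0.2% to 38.5%). Replaced by a normal retest, it gives 0/12 = 0% (exact 95% CI 0% to 26.5%).

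**Step 3. Effect of one QTcF reading.** The timepoint mean changes by (first reading − retest)/12. For assumed differences of 20, 40 and 60 msec in one patient:

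- 20/12 = 1.7 msec
- 40/12 = 3.3 msec
- 60/12 = 5.0 msec

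**Step 4. Sensitivity to the retest rate.** All inputs here are assumptions. Let p = 10% of first values be out of range on one side, and let a fraction f of those be retested at the same timepoint. First value and retest are taken as bivariate normal with correlation r and the same mean. The probability that both are abnormal, p11, is then 3.24%, 4.68% and 6.89% for r = 0.5, 0.7 and 0.9. The reported rate is p − f × (p − p11).

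| Fraction retested | r = 0.5 | r = 0.7 | r = 0.9 |
|---|---|---|---|
| 10% | 9.3% | 9.5% | 9.7% |
| 25% | 8.3% | 8.7% | 9.2% |
| 100% | 3.2% | 4.7% | 6.9% |

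Example: f = 25%, r = 0.5 gives 10 − 0.25 × (10 − 3.24) = 8.3%. The loss is small if retests are rare and large only if nearly every abnormal value is retested. The documents do not show which case applies.

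**The case against.** The strongest defence is that this is a disclosed convention in a 12-patient, open-label, exploratory study with descriptive statistics, daily safety review and full listings. No decision rule depends on the lab shift table. The rule is also symmetric, because baseline is the last predose value as well. Replacing the last value throughout with a first or worst value would break that symmetry and could create apparent shifts, and the full panel is not drawn in the placebo cycle to calibrate them. This stands. It is the reason to add a table and leave the existing ones unchanged.

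Three stronger readings are tempting, and the documents do not support them.

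- A reader might infer that a normal retest removes the abnormality from every summary. It does not. Blood pressure and pulse values all count towards Table 3. Lab and ECG changes judged clinically significant or needing intervention are to be reported as AEs (Protocol 3.7.3.7) and can then reach the TEAE tables. There is no QTcF shift table to lose a value from.
- A reader might see a conflict with the protocol's repeat-ECG rule. That rule says "the average of the 3 QTcF values will be used to determine the patient's eligibility" and is confined to eligibility. It says nothing about postdose tracings. Averaging repeats on drug would also dilute an extreme first reading.
- A reader might infer that a later retest, taken after the drug has worn off, will overwrite the Discharge sample and hide most drug-related abnormalities. The repeat provisions for out-of-range results concern eligibility. There is no postdose retest rule, and the SAP sets assessment windows only for ambulatory blood pressure. A retest on another day need not be assigned to Discharge, and the text available gives no half-life from which to judge what drug effect would remain.

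**Conclusion.** The point holds in limited form. The all-values safeguard in SAP 9.1 has no lab or QTcF criteria behind it. An abnormal result therefore appears only in listings when two conditions are met: a retest assigned to the same timepoint is normal, and the abnormality is not reported as an AE.

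Where retests follow abnormal results, the direction is towards no effect. The total size cannot be determined, because the postdose retest frequency is not stated. Per event, one value is worth 8.3 percentage points in a shift-table entry, assuming 12 patients have data, or one twelfth of the difference between the two readings in a QTcF mean. The percentages in Step 4 illustrate sensitivity to assumed inputs and do not estimate what will happen in this study.

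This is a modest reporting gap and does not undermine the study. It is worth closing because safety is the first objective and the remedy extends a principle the SAP already applies to blood pressure and pulse.

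**What to change.** Keep the by-timepoint tables as they are. Add the following to SAP 7.9.2, 7.9.4 and 9.1, and record the additions in SAP 8.

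- **Labs:** a shift table from baseline to the lowest and to the highest postbaseline value for each patient, using all scheduled, repeat and unscheduled results except samples documented as invalid. Fasting glucose and insulin are drawn in every cycle, so present these two by cycle, with the placebo cycle as reference.
- **QTcF:** each patient's maximum postdose QTcF and maximum change from study baseline, by cycle, from all tracings. Study baseline is the practical reference because an unscheduled tracing has no time-matched placebo value. Showing the placebo cycle alongside gives a comparator.
- **Footnote:** state that a worst postbaseline value is compared with a last-value baseline, so some excess of abnormal results is expected even without a drug effect.

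The cost is a few SAP sentences and some extra programming, with no new data collection. The drawback is a somewhat higher abnormal count, which the footnote explains.

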9.2 CONVENTIONS FOR SUMMARIZING ADVERSE EVENTS

The following conventions will be followed in summarizing TEAEs within a cycle group:

- For patient incidence summaries by cycle group, each patient will be counted only once within each SOC, PT, or the overall AE summary within each cycle
- If a patient reported more than one AE within an SOC or PT within a particular cycle, then the TEAE with the highest severity or strongest study drug relationship within each SOC and each PT will be included in the summaries by severity or relationship, respectively.

9.3 MISSING DATE INFORMATION FOR ADVERSE EVENTS

If it is not possible to determine when an AE started due to incomplete start dates/times, it will be assumed to be treatment emergent.

9.4 MISSING SEVERITY ASSESSMENT FOR ADVERSE EVENTS

If severity is missing for an AE that started prior to the dosing of study drug, all efforts should be made to obtain the severity from the Investigator. If it is still missing after all efforts, then a severity of “Mild” will be assigned. If the severity is missing for an AE that started on or after the date of dosing of study drug, then a severity of “Severe” will be assigned. The imputed values for the missing severity assessment will be used for the incidence summary, while the actual missing values will be presented in data listings.

9.5 MISSING RELATIONSHIP TO STUDY DRUG FOR ADVERSE EVENTS

If the relationship to study drug is missing for an AE that started on or after the date of dosing of study drug, all efforts should be made to obtain the date from the Investigator. If it is still missing after all efforts, a causality of “Related” will be assigned in the corresponding analysis-derived data set. The imputed values for the missing relationship to study drug will be used only for incidence summary, while the actual missing values will be presented in data listings.

9.6 MISSING DATE INFORMATION FOR PRIOR OR CONCOMITANT MEDICATIONS

If the start date of a medication is missing or incomplete (i.e., partially missing), then the medication will be assumed to be concomitant.

9.7 ASSESSMENT TIME WINDOWS FOR AMBULATORY BP ANALYSIS

Table 4 presents the timepoints used for the ambulatory BP analysis and the corresponding assessment windows during which the actual assessment may have occurred.

Table 4 . Timepoint Windows for Ambulatory BP Analysis

| Postdose Timepoints | Assessment Window [1] |
|----------------------------|---|
| 30 min postdose | dosing to 0.5h + 15min on Cycle Day 2 |
| 1 h postdose | 1h ± 15min on Cycle Day 2 |
| 1.5 h postdose | 1.5h ± 15min on Cycle Day 2 |
| ... | ... |
| 12 h postdose | 12h - 15mins to 12h postdose on Cycle Day 2 |

[1] Postdose timepoints are relative to dosing time on Cycle Day 2.

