4. DETERMINATION OF SAMPLE SIZE

The sample size in this trial was determined outside of statistical considerations. A sample size of 12 patients is considered sufficient and is based on precedent set by prior studies of similar nature.

**5. PHARMACOKINETIC, PHARMACODYNAMIC, AND
SAFETY ASSESSMENTS**

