6.3 HANDLING OF DROPOUTS OR MISSING DATA

Missing observations will be treated as missing at random, and no imputation will be performed. All safety and tolerability data will be summarized and analyzed when data values are available for a patient. With respect to PK data, parameters will be derived as defined in Section 5.3 and although these methods may employ some inherent estimation of missing values (i.e., calculation of AUC), no formal imputation methods will be performed for the study.

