7.7 PHARMACODYNAMIC (PD) ANALYSIS

7.7.1 PD Parameters

The pharmacodynamic parameters are described below:

Ambulatory BP Monitoring

- Change from time-matched baseline in average daytime systolic BP, MAP, diastolic BP, and pulse. The daytime average for any IW-1973 cycle is defined as the average of the 30-minute average ambulatory assessments from the time of dosing on the ABPM assessment day to the end of the 12-hour ABPM recording for that cycle. Time-matched baseline is defined as the average of ambulatory assessments from the time of dosing on the ABPM assessment day of the Placebo cycle (Study Day 2) to the end of the 12-hour ABPM recording.
- Change from time-matched baseline in average daytime systolic BP, MAP, diastolic BP, and pulse by race (blacks vs. non-blacks)
- Change from time-matched baseline in 4-hour averages of MAP, systolic BP, diastolic BP, and pulse. The 4-hour averages are calculated from the time of dosing on the ABPM assessment day, using the 30-minute average values. Baseline is defined as the corresponding 4-hour average on Day 2 of the placebo cycle.

- Change from time-matched baseline in systolic BP, diastolic BP, MAP, and pulse at 30-minute postdose intervals. See Section 9.7 for details on calculation of assessment time intervals. Baseline is defined as the corresponding 30-minute average on Day 2 of the placebo cycle.

Supine Pulse and BP Measurements

- Change from study baseline in supine systolic BP, diastolic BP, and pulse
- Change from time-matched baseline (placebo cycle) in supine systolic BP, diastolic BP, and pulse
- Change from cycle baseline in supine systolic BP, diastolic BP, and pulse
- Change from trough baseline in trough systolic BP, diastolic BP, and pulse. The trough value for each cycle is defined as the 24 hour postdose assessment after the last dose of that cycle. Trough baseline is the last assessment prior to initiation of IW-1973 administration, that is, the Study Day 4 predose assessment
- Change from pre- to post-nitroglycerine dose assessments of supine systolic BP, diastolic BP, and pulse at the follow-up visit

Orthostatic BP Measurements

- Orthostatic changes in systolic BP, diastolic BP, and pulse. An orthostatic measurement is obtained by subtracting the supine measurement from the standing measurement.

Endothelial Function Assessments

- Change from study baseline in RHI
- Change from time-matched baseline (placebo cycle) in RHI
- Change from cycle baseline in RHI

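### SAP Table 4 makes the first 30-minute ABPM window 45 minutes wide and the last one 15, so the 12 h change rests on about half the readings of an interior timepoint.

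*SAP*

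**What the plan says.** SAP Section 7.7.1 lists among the ambulatory parameters: "Change from time-matched baseline in systolic BP, diastolic BP, MAP, and pulse at 30-minute postdose intervals". It refers to Section 9.7 for the intervals. On the comparator it says: "Baseline is defined as the corresponding 30-minute average on Day 2 of the placebo cycle". On the longer blocks it says: "The 4-hour averages are calculated from the time of dosing on the ABPM assessment day, using the 30-minute average values".

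Table 4 in Section 9.7 gives the windows:
- 30 min timepoint: "dosing to 0.5h + 15min on Cycle Day 2"
- 1 h timepoint: "1h ± 15min on Cycle Day 2", with 1.5 h on the same pattern and an ellipsis for the rest
- 12 h timepoint: "12h - 15mins to 12h postdose on Cycle Day 2"

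The protocol (Schedule of Events and Section 3.8.2.3) has recording start no more than 30 minutes before dosing and end at 12 h after dosing, with a tolerance of plus 30 minutes. SAP Section 5.2 describes it as a 12-hour recording. On missing data, SAP Section 6.3 says: "Missing observations will be treated as missing at random, and no imputation will be performed". Neither document gives the interval between readings or a minimum number of readings per window.

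**The concern.** The plan reports these values as 30-minute averages, yet the two end windows have other lengths, and the short one sits at the latest ambulatory timepoint. A change at 12 h needs a reading in the 15-minute window in both the placebo and the drug recording. If either window is empty, there is no value.

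The point is used twice beyond the tables. SAP Section 7.7.3 plots mean 30-minute changes with 95% confidence intervals by cycle. SAP Section 7.8.4 plots 30-minute changes against plasma concentration at the same nominal time. Postdose PK samples within the recording span are scheduled only at 1, 3, 6 and 12 h (Protocol Section 3.8.2.2), so 12 h is one of four matched points and the only late one.

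Two smaller issues follow from the same table. A reading exactly on a shared endpoint belongs to two windows, and no rule assigns it. The 4-hour averages also inherit the uneven windows.

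**Working it through.** There is no stated precision or yield figure to reproduce. SAP Section 4 says of the 12 patients: "The sample size in this trial was determined outside of statistical considerations".

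**Window widths (Table 4, reading the ellipsis as a continuation of the pattern)**
- First: 0 to 45 min = 45 min
- Interior: 1 h to 11.5 h, 22 windows of 30 min = 660 min
- Last: 11:45 to 12:00 = 15 min
- Total: 45 + 660 + 15 = 720 min, so the 24 windows cover 0-12 h without a gap

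**Four-hour blocks (eight windows each)**
- 0.5 to 4 h: 0:00 to 4:15, length 4:15
- 4.5 to 8 h: 4:15 to 8:15, length 4:00
- 8.5 to 12 h: 8:15 to 12:00, length 3:45

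**Readings at 12 h.** With one reading every d minutes, the expected count is 15/d at 12 h and 30/d at an interior point, a ratio of one half. At d = 15 that is one reading instead of two. The reading-to-reading part of the SD is then √2 = 1.4 times larger, if readings are independent.

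**Availability of a 12 h pair.** Assumptions: regular readings from the start of recording, with the start uniform over the permitted 0-30 min before dosing. Let p be the chance that one recording has a reading in the window. The paired share is p² if the two cycles have independent start times and p if they have the same one.

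| Reading interval (assumed) | Starts that miss the window | p | Paired share, p² to p | Of 12 patients |
|---|---|---|---|---|
| 15 min or less | none | 1.00 | 100% | 12 |
| 20 min | 15-20 min before dosing | 25/30 = 0.83 | 69-83% | about 8 to 10 |
| 30 min | 15-30 min before dosing | 15/30 = 0.50 | 25-50% | 3 to 6 |

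A simulation of 100,000 recordings agrees: p = 1.000, 0.833 and 0.499.

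**Effect on the 12 h confidence interval at the same SD.** The half-width is proportional to t/√n.
- n = 12: 2.201/√12 = 0.635
- n = 6: 2.571/√6 = 1.050, or 1.65 times as wide
- n = 3: 4.303/√3 = 2.484, or 3.9 times as wide

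**Daytime mean.** Section 7.7.1 defines the drug-cycle value as an average of 30-minute averages, but the placebo baseline as an average of the ambulatory assessments. Read literally, with evenly spaced readings:
- First 45 min: weight 1/24 = 4.2% on drug, 45/720 = 6.25% on placebo
- Last 15 min: weight 1/24 = 4.2% on drug, 15/720 = 2.1% on placebo

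About two percentage points of weight move at each end, so the effect is small.

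**The case against.** The strongest reply is that little depends on this. The same windows apply in the placebo and drug cycles, so unequal widths do not by themselves bias a 30-minute or 4-hour time-matched difference. If the 12 h window is empty, the last 4-hour average loses one of eight components and the daytime average one of 24. The SAP treats inference as descriptive (Section 6.1) and stresses estimation (Section 6.6). The 11.5 h window is full width, and cuff blood pressure is also taken at 12 h on the first day of each cycle. All of that stands and limits the weight of the point.

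A reader might infer that the 12 h change will exist for only a quarter to a half of patients. The documents do not support that as a general statement. It needs readings every 30 minutes or longer, and the interval is not given. The wording about 30-minute averages fits more than one reading per window, though it does not prove it. Even at 30-minute readings, a recording started 0-15 min before dosing always fills the window.

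A reader might also infer widespread double counting. With 15-minute readings exactly aligned to dosing, 23 of 48 would fall on a shared endpoint, but recording starts at a variable time before dosing, so such alignment is not planned. The missing tie rule is a gap that a programming convention closes.

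Nor is stopping at 12 h an error in itself, since it gives every recording the same coverage. The weakness is that the cut halves a window that the permitted recording could have filled.

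**Conclusion.** The labelling fault is in the text and needs no assumption beyond the ellipsis: windows of 45, 30 and 15 minutes are all treated as 30-minute averages, endpoints are shared, and the 4-hour averages cover 4:15, 4:00 and 3:45. With regularly spaced readings, the 12 h point has on average half the readings of an interior point. How many patients have a 12 h pair depends on the unstated reading interval and on the start-time assumption. Across intervals of 30 minutes or less, the share runs from 25% to 100%.

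The consequence is weaker precision, and possibly missing values, at one of 24 descriptive timepoints that is also the only late PK-matched ambulatory point. It is not a material bias in the time-matched differences. The correction is worth making because it is cheap, not because the study's conclusions hang on it.

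**What to change.** 1. Keep the centred windows and make them half-open, from t - 15 min up to but not including t + 15 min, so that each reading belongs to one window. If the 0.5 h window stays at 45 minutes, say so in the table.
2. Extend the 12 h window to 12 h + 15 min, using readings the protocol already allows. If both recordings run to at least 12 h 15 min, every patient has a pair at any interval of 30 minutes or less. If the end varies uniformly over 12-12.5 h and start times are independent, p at 30-minute readings is 0.5 + 0.5 × 0.75 = 0.875, so pairs rise from 25% to 0.875² = 77%. At 20 minutes they rise from 69% to 97%.
3. Compute the 4-hour and daytime averages directly from readings in 0-4, 4-8, 8-12 and 0-12 h, in the same way in the placebo and drug cycles.
4. State the reading interval, and report the number of pairs at each timepoint.

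Equal bins (0, 0.5 h] to (11.5, 12 h] are an acceptable alternative. They give exact 4-hour blocks and always contain a scheduled reading at intervals of 30 minutes or less. They also move the 22 interior windows 15 minutes earlier relative to the nominal PK times in Section 7.8.4, and that shift would have to be accepted and stated.

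The cost is one SAP table with its program and the matching definitions in Section 7.7.1, with no new data. The remaining downside is that the 12 h window is full width only where the recording runs to 12 h 15 min.
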